18.1.2 OVERALL

The **sponsor** has the right to discontinue the trial due to relevant medical or administrative reasons.

Possible reasons for discontinuation by the sponsor are:

- failure in recruiting participants,
- insufficient data quality,
- unforeseen circumstances at the trial site that make the continuation of the trial impossible,
- occurrence of unjustifiable risks or toxicity,
- new scientific knowledge that does not justify continuation of the clinical trial.

Trial discontinuation will be decided by the sponsor in cooperation with the investigator.

18.2 PROCEDURES FOR PREMATURE TERMINATION OR SUSPENSION OF A SINGLE SITE

The sponsor has also the right to discontinue the participation of a site for one of the following reasons:

- failure in recruiting participants
- insufficient data quality
- no adherence to the protocol.

18.3 PROCEDURES FOR PREMATURE TERMINATION OR SUSPENSION

The responsible ethics committee will be informed of the situation and the reason for the decision. The sponsor will pick up the study equipment and the investigator has to complete the documentation.

A final report will be created on the basis of the contained data.

19 PLANNED TERMINATION OF CLINICAL INVESTIGATION

The clinical investigation report should be provided to the EC's within 12 months after study termination. Planned Study termination will defined as last patient last visit (LPLV).

20 DATA SECURITY AND PUBLICATION POLICY

20.1 PATIENT IDENTIFICATION AND CONFIDENTIALITY

Within this study, personal data from the investigation subjects (name, initials, date of birth) and data regarding the therapy and the course of disease (medical results, types of therapy) will be collected in the trial site. The identity of subjects enrolled in the study and the information contained in their study records will be kept confidential. The data will be stored and processed in pseudonymized form (i.e. without reference to the patient's name) with the aid of an identification number.

Since in the course of the investigation contact between the trial site and the patients is necessary, the patients' full name, address and telephone number will be ascertained and stored after obtaining written permission to do so. This information will be stored separately from the investigation data.

Data will be analysed at the KKS Dresden. The safety concept ensures amongst other things that data access is limited to authorized persons, that measures are taken to prevent loss of data and that the laws pertaining to data protection are observed. The data are protected from third party access and only members of the investigation are permitted access. These members are sworn to secrecy.

In the event of withdrawal of consent, the investigation subject's stored data must be deleted if this is requested by the subject.

20.2 DECLARATION REGARDING DATA PROTECTION

During data entry, processing and analysis in the KKS Dresden, [name], all requirements of the data protection act will be taken into account. Access to the data is strictly limited to authorized persons. Data are protected against unauthorized access.

20.3 DECLARATION REGARDING THE PSEUDONYMIZED TRANSFER OF PERSONAL DATA

The sponsor certifies herewith that the transfer of pseudonymized personal data will take place according to the documentation and communication regulations in MPKPV-guideline §10 (5). Moreover, the sponsor certifies that persons who do not permit the transfer of data will not be admitted to the investigation.

23.1 Clinical Usability Questionnaire

Note:

This test specification is intended to validate the clinical usability of the information on ventilation distribution and lung volume changes which is displayed by PulmoVista 500.

Please respond the following questions in eCRF if this not interfere your clinical routine.

1. Select the View "**Main**".

How easy is it to identify within the **Tidal Image**, whether the right and the left lung are evenly ventilated?

2. Select the View "**Main**".

How easy is it to quantify the regional ventilation distribution as expressed by the regional parameters **TV ROI 1 - TV ROI 4**?

3. Select the view "**End-Insp. trend**",

Put cursor **C1** before and cursor **C2** after the intervention; View the differential image and the parameters in the trend table.

How easy is it to set the cursors to respective positions which allow you to compare ventilation distribution before and after the intervention?

4. Select the view "**End-Insp. trend**",

Put cursor **C1** before and cursor **C2** after the intervention; View the differential image and the parameters in the trend table.

How easy is it to detect increases and/or decreases of regional ventilation?

5. Select the view "**End-Insp. trend**",

Observe the global impedance waveform, and the graphical Medibus trend below the waveform and the trend table.

How easy is it to relate the regional ventilation distribution and the corresponding parameters from the ventilator to each other?

6. Select the view "**End-Insp. trend**",

Put cursor **C1** before and cursor **C2** after the intervention; View the differential image and the parameters in the trend table.

How useful is the clinical information on ventilation redistribution caused by this intervention?

7. Select the view "**ΔEELI trend**",
Put cursor **C1** before and cursor **C2** after the intervention; View the differential image and the dEELI parameters.
How easy is it to set the cursors to respective positions which allows you assessing lung volume changes induced by the intervention?
8. Select the view "**ΔEELI trend**",
Put cursor **C1** before and cursor **C2** after the intervention; View the impedance waveforms, the differential image and the dEELI parameters.
How easy is it to detect increases and/or decreases of regional lung volume?
9. Select the view "**ΔEELI trend**",
Put cursor **C1** before and cursor **C2** after the intervention; View the differential image and the dEELI parameters.
How useful is the clinical information on regional lung volume changes caused by this intervention?

23.2 Clinical Plausibility Questionnaire

Questions addressing the regional aspects of the secondary endpoints

One of the major purposes of the pivotal clinical study

Assessment of the capability of PulmoVista 500 to continuously monitor changes of ventilation over time is to assess the plausibility of the regional information, which cannot be validated by CT scans.

The following questions are intended to validate, whether

- the regional information provided by PulmoVista 500 is plausible in the presence of certain lung conditions, which are visible in CXR or lung CT and known to cause poor ventilation
- PulmoVista 500 is capable of displaying changes of lung conditions induced by therapeutic interventions
- those changes are plausible and correspond to the information that an experienced user would expect based on his knowledge about lung physiology

Please respond the following questions in eCRF if this does not interfere with your clinical routine.

1. Select the view „**Main**“.
Does the **Tidal Image** indicate poorly or non-ventilated lung regions and does this location approximately match with those regions, where CXR or lung CT shows either lung collapse, atelectasis or pleura effusion?

2. Select the view "**Main**" and observe the Tidal Image, while one of the lungs is blocked.
Does the **Tidal Image correctly** indicate which side of the lung is not being ventilated?
3. Open the view "**dELLI trend**" after the PEEP setting has been changed. Set C1 at the lower and C2 at the higher PEEP level.
Does the image dELLI: C2 minus C1 show the expected increase of endexp.lung volume in turquoise (light blue) color?
4. Open the view "**End-insp. trend**" after the PEEP setting has been changed significantly (2 mbar or more). Set C1 at the lower and C2 at the higher PEEP level.
Does the image Change: C2 minus C1 and/or the corresponding regional Tidal Variations show the expected redistribution of ventilation from ventral to dorsal?
5. Open the view "**dELLI trend**" after lung suction has been conducted. Set C1 at a phase before and C2 during or immediately after the lung suction.
Does the image dELLI: C2 minus C1 show the expected decrease of lung volume in orange color?
6. Select the view "**Main**" and observe the Tidal Image from a patient with pneumonectomy.
Does the Tidal Image properly indicate the non-ventilated lung regions and does the location approximately match with those region, where the lung has been removed?

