6.1.2 BLINDING

This is an observational trial of intraindividual correlation between two methods of measurement. Since we do not allocate patients to treatment and placebo groups as it would be the case in a randomized trial, blinding is not strictly necessary. However, patients will be blinded to the results of the investigational EIT device by either a) being sedated in the ICU or under general anesthesia or b) device will not be facing them so they cannot see the results.

Study personnel at bedside will not be blinded as they have to interact with the device (to ensure quality of data recording) and therefore blinding is not feasible.

The medical personal responsible for the patient's medical care does not use the information given by the PulmoVista 500 .

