6.1.3 PRIMARY AND SECONDARY STUDY ENDPOINTS

PRIMARY STUDY ENDPOINT

The capability of PulmoVista 500 for continuous monitoring of ventilation and its changes at different points in time during varying states of regional ventilation, the cross-correlation function (CCF) between global tidal impedance (EIT) waveforms and global tidal volume (ventilator) curves will be evaluated.

SECONDARY STUDY ENDPOINTS

- First secondary endpoint: To assess the capability of PulmoVista 500 to detect changes in regional ventilation by evaluating the cross correlation between impedance waveforms derived from PulmoVista 500 and volume curves derived from ventilator during one-lung-ventilation.
- Assess that changes of tidal volumes induced by ventilator settings can be monitored by the "Trends view"
- Assess that changes of the end-expiratory lung volumes (induced by e.g. PEEP changes, recruitment and suctioning maneuvers) can be monitored by "dELLI trend view"

- Documentation of any safety events related to the use of PulmoVista 500
- Assessing the use specific clinical helpfulness of PulmoVista 500 - clinical helpfulness of PulmoVista 500 is proven if
 - see attachments (chapter 23.1) clinical usability

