6.4.2 VISIT 2 - MEDICAL AND STUDY MEASUREMENT

6.4.2.1 PATIENTS CURRENTLY ON OR SCHEDULED FOR VENTILATOR CARE IN THE ICU

The physicians responsible for the patients' medical care will inform the study team when the actual medical intervention is planned. Study team will re-evaluate whether all in- and exclusion criteria are appropriately met (e.g. still intubated).

Study team will setup the investigational devices at least 30 minutes before the medical intervention to allow for stable baseline readings and uninterrupted medical care. PulmoVista 500 electrode belt is placed around the patient's chest, and the PulmoVista 500 is connected to the ventilator. Continuous recording of data is started and verified.

During the investigational phase, the study device will continuously record all data. Before the study measurement, the study team will record baseline readings for at least 5 minutes. During the study measurement, recording will continue uninterrupted; exact time points of events (e.g. when vent settings are adjusted) and details of the study measurement (e.g. old and new vent settings) are recorded by the study personnel according to the clock in PulmoVista 500 (to ensure accurate timing with the recorded data). Recording of the data will continue for at least 5 minutes after the medical intervention is completed.

Once the recording is completed, electrode belt will be removed from the patient and the investigational device will be disconnected.

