1.1 STUDY OBJECTIVE

PulmoVista 500 is a lung function monitor for clinical use which continuously generates cross-sectional images of the lung function by applying the technique of electrical impedance tomography (EIT).

To perform bioimpedance measurements, an electrode belt containing 16 electrodes is placed around the chest wall. Additionally, one reference electrode must be attached to a central point to the body, preferable on the abdomen. The reference electrode ensures that all measurements at different electrode pairs are referenced to the same electric potential¹. PulmoVista 500 provides graphical information about the regional distribution of ventilation and changes of end-expiratory lung volume. The spatial resolution of this information allows continuously observing specific conditions of different lung regions.

The primary objective of this study is to assess the capability of PulmoVista 500 to continuously monitor ventilation and changes of lung volume

For this propose cross-correlations between the global impedance waveforms created by a ventilator shall be evaluated.

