3.3 SECUNDARY STUDY OBJECTIVES

3.3.1 Efficacy

- To demonstrate the ability of PulmoVista 500 to display regional ventilation changes, a quantitative evaluation is performed using the cross-correlation coefficient between the impedance waveforms of PulmoVista 500 and the ventilator volume waveforms in the subgroup of OLV patients.
- To evaluate Pulmo Vista 500's monitoring features, it assesses whether changes in tidal volumes induced by ventilation settings are represented by the "main view". For this purpose, the plausibility questionnaire is evaluated.

- Assess that changes of the end-expiratory lung volumes (induced by e.g. PEEP changes, recruitment and suctioning maneuvers) can be monitored by “dEELI trend view”. The plausibility questionnaire is also evaluated for this.
- To evaluate the clinical usefulness of PulmoVista 500, the questionnaire on clinical utility across all patients is evaluated.
- In order to demonstrate the ability of PulmoVista 500 to produce controlled induced regional changes, an evaluation is performed using the OLV subgroup. Three blinded rater evaluate the corresponding waveforms.

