From this table, the success rate $(a + d) / (a + b + c + d)$, the sensitivity $a / (a + b)$, the specificity $d / (c + d)$ and the corresponding confidence intervals are calculated. The reverence (real side of the ventilation) is taken in the study documentation (e.g. Name of corresponding Marker and/or MACRO Database) of the individual patients.

- To assess the ability of PulmoVista 500 to display changes in ventilation-induced tidal volumes through the "Trend View", the plausibility questionnaire across all patients is evaluated. The questions of the plausibility questionnaire in relation to the "main view" are individually counted according to their categories (yes / no / n.a.) and listed as a percentage.
- To assess the ability of PulmoVista 500 to display changes in end-expiratory lung volumes (induced by e.g. PEEP changes, recruitment and suction maneuvers) using the "dELLI Trend View", the plausibility questionnaire is evaluated across all patients. The questions of the plausibility questionnaire in relation to the "dELLI trend view" are individually counted according to their categories (yes / no / n.a.) and listed as a percentage.
- The evaluation of clinical usefulness, the nine questions of the questionnaire on clinical usefulness, are individually counted according to their category level (1 very difficult ... to ... 5 very useful) and listed on a percentage basis. Furthermore, the mean and standard deviation are calculated for each of these nine questions.

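### The end-expiratory lung-volume endpoint rests only on cued yes/no answers with no no-change comparison, and SAP 1.1 moves lung-volume change into a primary objective that the cross-correlation cannot assess

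*Protocol*

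**What the plan says.** Protocol 6.1.3 lists this secondary endpoint: "Assess that changes of the end-expiratory lung volumes (induced by e.g. PEEP changes, recruitment and suctioning maneuvers) can be monitored by" the dEELI trend view. SAP 3.3.1 names one data source for it: "The plausibility questionnaire is also evaluated for this". Under SAP 5.6.1 the relevant answers "are individually counted according to their categories (yes / no / n.a.) and listed as a percentage".

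Two items in Protocol 23.2 use the dEELI view. Item 3 concerns PEEP. It instructs the respondent: "Set C1 at the lower and C2 at the higher PEEP level", and then asks: "Does the image dELLI: C2 minus C1 show the expected increase of endexp.lung volume in turquoise (light blue) color". Item 5 concerns suction. It places C1 before and C2 during or just after the manoeuvre, and asks whether the expected decrease appears in orange.

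On who sees what, Protocol 6.1.2 says: "Study personnel at bedside will not be blinded as they have to interact with the device". On what is recorded before an ICU intervention, Protocol 6.4.2.1 says: "Before the study measurement, the study team will record baseline readings for at least 5 minutes".

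SAP 1.1 states: "The primary objective of this study is to assess the capability of PulmoVista 500 to continuously monitor ventilation and changes of lung volume". It then says that cross-correlations serve this purpose. Protocol 5.1.1 confines the primary objective to ventilation and its changes, and Protocol 5.1.2 puts lung volume among the secondary objectives.

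**The concern.** Both dEELI items tell the respondent which direction and colour to look for, and the respondent sets the cursors around a known intervention. Nobody reads an interval in which nothing was changed. The plan therefore records how often a cued reader agrees with the expected picture. It does not record how often the same reader would agree when there was nothing to see.

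The plan is stricter elsewhere. Item 2 of the same questionnaire asks whether the blocked lung is shown correctly. For that question SAP 5.6.1 adds three blinded raters, a documented reference side, a 2x2 table and confidence intervals. The dEELI endpoint has no counterpart.

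SAP 1.1 adds a second problem. With lung-volume change inside the primary objective, the primary analysis appears to cover something that it does not measure. At stake is what the study can claim about end-expiratory lung volume. Protocol 3.2 intends the data to support authorization in other countries, and Protocol 23.2 calls the study pivotal.

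**Working it through.** **1. Is there a planned figure to reproduce?** Not for this endpoint. The documents give it no sample size, expected rate or threshold, and Protocol 7.3 sets no pass/fail criterion. The trial's 68 evaluable patients do reproduce from Protocol 7.1: a one-sample t-test with d = 0.1/0.25 = 0.4, two-sided 0.05 and power 0.9 gives n = 68 (power 0.902), and 68/0.85 = 80. That calculation concerns the mean cross-correlation coefficient, not dEELI.

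**2. What the percentage estimates.** Let s be the probability of yes when a change was made, and f the probability of yes when none was made. The plan observes s only. Discrimination is s − f. With an assumed s = 0.90:

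| Assumed f | s − f |
|---|---|
| 0 | 0.90 |
| 0.3 | 0.60 |
| 0.5 | 0.40 |
| 0.9 | 0 |

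More answers narrow the interval around s but say nothing about f. The exact 95% interval is about 73% to 98% for 27/30 and 77% to 96% for 42/47. (55 planned ICU patients × 0.85 ≈ 47. The number of PEEP steps and suctions is not stated.)

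**3. Can the primary analysis cover the gap?** There are two separate reasons why it cannot.

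- *The offset is removed.* SAP 7.2 exports one minute before and one minute after the intervention. It correlates Global with Volume in each file separately and averages the two results. A correlation is unchanged by adding a constant: r(Global + δ, Volume) = r(Global, Volume). If the post-intervention impedance level shifts by δ, the post coefficient and the average stay the same. That shift is what dEELI is meant to show.
- *The reference has no end-expiratory level.* In the example export in SAP 7.2 the ventilator volume runs 53, 44, 38, 29, 22, 14, 9, 3, 0, 0, 0, 0, 13, 52. At the first three zeros the airway-pressure column still reads 15.1 to 15.2 mbar, so zero is the start point of the breath and not a measure of the gas left in the lung. This is one illustrative breath, but the first reason does not depend on it.

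**4. Is a control feasible?** At least five minutes of unchanged ICU baseline are recorded. In the SAP 7.2 example the pre and post files are minutes 3 and 5, with one minute between them. Five baseline minutes contain three pairs with that spacing: 1 and 3, 2 and 4, 3 and 5.

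For scale, comparing s = 0.9 with f needs the following readings per condition (two-sided 0.05, power 0.9, independent readings, pooled normal approximation):

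n = [1.96·√(2p̄(1−p̄)) + 1.28·√(s(1−s) + f(1−f))]² / (s−f)², with p̄ = (s+f)/2

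This gives 6, 12, 26 and 82 for f = 0.1, 0.3, 0.5 and 0.7. Worked for f = 0.5: (1.270 + 0.747)²/0.16 ≈ 25.4, so 26.

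For sign agreement tested against 50% (exact, one-sided 0.025), at least 21 of 30 is needed (power 0.94 if true agreement is 0.8), or 31 of 47 (power 0.99). The 50% assumes that drift is unrelated to the direction of the step. All rates here are assumptions.

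**The case against.** The other side has several good points.

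- **The items can fail.** A reader might infer that a display stuck on one colour would score perfectly, or that the endpoint can only be confirmed. The documents do not support either. Items 3 and 5 expect opposite colours on a subtraction image and are counted separately, so one constant colour fails one of them. No is an available answer.
- **Item 3 already aligns signs.** C1 goes to the lower PEEP whatever the time order. One-directional drift would favour yes after increases and no after decreases. Drift matters more directly for item 5, where C1 always comes first. The documents give no size for drift.
- **The respondent is inferred.** Protocol 23.2 does not say who completes it. The bedside user is suggested by Protocol 6.1.2 and by the reference to the respondent's clinical routine. What is certain is that no blinded reader is assigned.
- **The instrument is labelled plausibility.** Its stated yardstick is an experienced user's expectation, and no test is planned. Reported in those terms, the percentages are coherent.
- **SAP 1.1 is one sentence.** SAP 3.2.1, 3.3.1 and 5.6.1 keep end-expiratory volume secondary. A reader might infer that a significant cross-correlation would be reported as proof of lung-volume monitoring. Nothing in the documents says so.

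These points limit the claim but leave its core. The endpoint is worded as a capability of the device and its only evidence is cued opinion. The contrast between items 3 and 5 does not supply f: both directions are disclosed, answering is optional, and no pairing within patients is planned.

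**Conclusion.** The point holds in a limited form. The dEELI percentages can show that users found the display plausible. They cannot by themselves show that end-expiratory lung-volume change can be monitored, because the false-yes rate is not observed at any sample size. The size of any reader bias or drift cannot be taken from the documents, so the table above shows only how wide the uncertainty is.

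Separately, SAP 1.1 is wrong as written. It disagrees with Protocol 5.1.1 and 5.1.2, and it attaches to the cross-correlation an end-expiratory shift that the calculation removes. This is a wording fault to correct, not evidence of an intended claim.

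The endpoint is secondary and the primary test is unaffected. The change is worth making because it is cheap and alters what the study can conclude on this endpoint.

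**What to change.** 1. **SAP 1.1:** restore the primary objective of Protocol 5.1.1, so that lung-volume change stays secondary.
2. **SAP 5.6.1:** add a supplementary analysis of the stored waveforms.
   - First confirm that the exported minutes share one impedance baseline, for example by loading them as one sequence.
   - Take the end-expiratory Global values (the minima flagged in the Min/Max column) before and after each marked PEEP change. Report how often the sign agrees with the documented direction, with a confidence interval that allows for several steps per patient. Show PEEP increases and decreases separately.
   - For suction, use the window that item 5 states, during or immediately after. A full-minute average could miss a brief fall.
   - Apply the same calculation to two no-change segments of the five-minute ICU baseline, spaced as closely as possible to the actual pre/post gap. Report how often the change after a step exceeds this drift. Where the actual gap is longer than the baseline allows, say that drift may be understated.
3. **Items 3 and 5:** keep them, reported as user-judged plausibility.

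The reference remains the direction of the documented change and not a measured end-expiratory volume. The analysis would therefore show directional response, not volume accuracy.

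The cost is SAP wording and some programming. If the shared baseline is confirmed, no new measurement and no change in care is needed. The result may be less favourable than the percentage of yes answers.
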